#### 15. Disease recurrence

Disease recurrence will be defined as the appearance of new SRF in a study eye after complete resolution of SRF at any point. The proportion of participants with disease recurrence will be described and time to disease recurrence will be compared between groups.

New variable	Rules
Disease recurrence (study eye)	YES: if complete resolution of SRF in study eye at any study visit = YES AND new SRF in study eye at any study visit after complete resolution = YES
	NO: if Complete resolution of SRF in study eye at any study visit = YES AND new SRF in study eye at any point after complete resolution = NO
	N/A: if complete resolution of SRF in study eye at all study visits = NO
	MISSING: otherwise

Time to disease recurrence

= (date of disease recurrence – date of disease resolution)

### 4.3 Other variables

Details for any other variables which will be derived for use in any other figures or tables are given below:

New variable	Rules
Exclusion category	INELIGIBLE: any of the inclusion criteria are NO, or any of the exclusion criteria are YES NOT APPROACHED: patient is eligible, patient approached = NO DID NOT CONSENT: patient is eligible, patient approached = YES, patient consented = NO DID NOT ATTEND SCREENING VISIT: patient is eligible, patient approached = YES, patient consented = YES, screening visit attended = NO INELIGIBLE POST-CONSENT: patient is eligible, patient approached = YES, patient consented = YES, screening visit attended = YES, patient consented = YES, screening visit attended = YES, patient consent = YES, screening visit attended = YES, but any of the post-consent inclusion criteria = NO, or any of the post-consent exclusion criteria = YES OTHER: patient is eligible, patient approached = YES, patient consented = YES, screening visit attended = YES, post- consent eligibility = YES, randomised = NO
Treatment received	YES: if at least one prescription has been completed NO: if no prescriptions have been completed
Age (years)	= (date of randomisation – date of birth)/365.25
Protocol deviation 1 – patient received the alternative drug to that allocated on at least one occasion	YES: if a bottle on any prescription does not match their treatment allocation NO: if all bottles on all prescriptions match their treatment allocation MISSING: otherwise
Protocol deviation 2 – patient did not meet eligibility criteria but was treated in the study	YES: if patient was ineligible at screening visit or at post- consent visit but was randomised NO: if patient was eligible MISSING: otherwise Note: if a patient who was otherwise eligible was ineligible due to an allergy to fluorescein or indocyanine green, a decision was made by the chief investigator to include them in the study, allowing them to take part in all aspects except for the FFA or ICGA imaging. These patients will not be classed as a protocol deviation.
Protocol deviation 3 – missed visit	YES: if patient attended visit = NO for any of the study visits before study exit) NO: if patient attended visit = YES for all study visits (before study exit) MISSING: otherwise

Protocol deviation 4 – visit attended but outside of study window	YES: if any visit attended falls outside the visit window NO: if all attended visits are within the visit windows MISSING: otherwise Visit windows: 1 week and restarting one week (+/- 1 day) 4 weeks and restarting four weeks (+/- 5 days) All other follow-up visits (+/- 10 days) Note: all visit windows are calculated from the date of randomisation, except re-starting visits which are calculated
Protocol deviation 5 – patient potassium exceeded 5.0mmol/L but patient was informed to continue treatment	YES: if patients potassium level was > 5.0mmol/L at any visit AND patient informed to continue treatment = YES NO: if patients potassium level was > 5.0mmol/L at any visit AND patient informed to continue treatment = NO OR patient potassium level ≤ 5.0mmol/L at all visits MISSING: otherwise
Protocol deviation 6 – incorrect dosage regimen followed	YES: if for any attended visit where the patient remained on the study treatment, the incorrect dose was prescribed. NO: if for all attended visits where the patient remained on the study treatment, the correct dose was prescribed. Correct dosage regimen: patient prescribed 25mg/day of treatment at baseline visit which is increased to 50mg/day after 1 week if the patients potassium level ≤ 5.0mmol/L. Patient continues on 50mg/day until there is evidence of complete resolution of SRF. If a patient restarts treatment during the study, the same dose escalation procedure will be followed i.e. patients will restart on 25mg/day increased to 50mg/day after 1 week.
Protocol deviation 7 – patient prescribed more bottles than required at study visit	
 
YES: if either:
 
Patient prescribed more than one bottle at baseline visit, 1 week visit or restarting visit
 
Patient prescribed more than two bottles at 4 week visit or restarting week 4 visit
 
Patient prescribed more than three bottles at 3 month, 6 month or 9 month visit
 
NO: if patient prescribed correct number of bottles at all study visits where treatment is continuing
 

Protocol deviation 8 – patients disease resolved but informed to continue treatment	YES: if at any study visit CSCR resolved = YES AND informed to continue treatment = YES NO: if either: • if CSCR resolved = NO at all attended study visits • if CSCR resolved = YES at any study visit AND informed to continue treatment = NO MISSING: otherwise
Systolic blood pressure (SBP)	
 
= SBP at screening visit if potassium results were back on day of screening visit
 
= SBP at baseline visit if potassium results were not back on day of screening visit
 

Diastolic blood pressure (DBP)	
 
DBP at screening visit if potassium results were back on day of screening visit
 
DBP at baseline visit if potassium results were not back on day of screening visit
 

Heart rate	
 
heart rate at screening visit if potassium results were back on day of screening visit
 
heart rate at baseline visit if potassium results were not back on day of screening visit
 

Study eye / non-study eye variables	For variables that are measured in right eye and left eye but are to be reported for study eye and non-study eye: STUDY EYE: If study eye = right eye then study eye variable = right eye measurement. Otherwise, if study eye = left eye then study eye variable = left eye measurement. NON-STUDY EYE: If study eye = right eye then non-study eye variable = left eye measurement. Otherwise, if study eye = left eye then non-study eye variable = right eye measurement.
Number of pills taken during time period	
 
= (Total number of pills prescribed during time period) – (Total number of pills returned in prescribed bottles collected on IMP database)
 
Note: if a bottle is confirmed as lost then it will be assumed that there were no pills remaining in the bottle
 

Number of pills expected to be taken during time period	
 
= (Date of next study visit) – (Date patient informed to start/continue treatment after current study visit)
 
If date patient informed to start/continue treatment is missing, then date of prescription will be used
 

Adherence for time period (for patients who received a prescription)	YES: if (number of pills taken during time period / number of pills expected to be taken during time period) *100 > 70 NO: if (number of pills taken during time period / number of pills expected to be taken during time period) *100 ≤ 70 MISSING: otherwise
Triiodothyronine (nmol/L)	Some triiodothyronine measurements have been recorded in pmol/L instead of nmol/L. To convert pmol/L to nmol/L: Triiodothyronine (nmol/L) = triiodothyronine (pmol/L) * 1000
Ta - Treatment and adherence indicator (for each post- randomisation study visit)	
 
= 1 if prescribed treatment in previous period and took >70% of pills expected
 
= 0 otherwise
 

Tna - Treatment and non- adherence indicator (for each post-randomisation study visit)	
 
= 1 if prescribed treatment in previous period and did not take
 
>70% of pills expected
 
= 0 otherwise
 

NTres – No treatment as resolved indicator (for each post-randomisation study visit)	
 
= 1 if at any point in previous period patient not on treatment as disease had resolved
 
= 0 otherwise
 

NToth – No treatment other reason indicator (for each post- randomisation study visit)	

= 1 if at any point in previous period patient not on treatment for any reason other than disease resolution

= 0 otherwise

Presence of granular/confluent hypoautofluorescence in the macula	Recorded directly as yes/no (SE_AF_GranularHypoAF) so no derivation required

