#### Table T10Study intervention

	Randomised to placebo (n=XX)	Randomised to eplerenone (n=XX)	Overall (n=XX)
Duration of treatment (months)			
Discontinued treatment as resolved			
Discontinued treatment for safety reason			
Resumed treatment			
Number of bottles confirmed as lost			
Notes:			

Data are presented as median (interquartile range), mean (standard deviation) or n (%).

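### Expected pills run to the next visit with no end at an instructed stop, so some participants who followed instructions are coded non-adherent

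*SAP*

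**What the plan says.** Section 4.3 of the SAP (Other variables) builds adherence from three pieces.

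- **Pills taken** are "Total number of pills prescribed during time period) – (Total number of pills returned in prescribed bottles collected on IMP database".
- **Pills expected** are "Date of next study visit) – (Date patient informed to start/continue treatment after current study visit". If the start/continue date is absent, a substitute applies: "If date patient informed to start/continue treatment is missing, then date of prescription will be used".
- **The classification** is headed "Adherence for time period (for patients who received a prescription". It returns NO when 100 times the ratio of taken to expected is 70 or less, and YES above that.

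The same section defines visit-level indicators. Tna is 1 "if prescribed treatment in previous period and did not take" more than 70% of the expected pills, and Ta is its adherent counterpart. NToth is 1 "if at any point in previous period patient not on treatment for any reason other than disease resolution", and NTres does the same for resolved disease.

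Other parts of the SAP recognise that treatment can be withheld or stopped. Protocol deviations 5 and 8 in section 4.3 use a recorded answer on whether the participant was told to continue. Table T10 counts stops for resolution and has a row "Discontinued treatment for safety reason". Section 5.3.6 splits each period into time on treatment and adherent, on treatment and non-adherent, off treatment because resolved, and off treatment for another reason. Its worked example puts 25% of a period in the first category and 75% in the third.

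**The concern.** The denominator is calendar time to the next visit and ignores the instruction to stop. A participant who did exactly as told can therefore fall below the 70% line only because treatment was halted early in the interval. The adherence tables by arm would then mix poor compliance with instructed interruption, and the exploratory adherence model would carry some of that mixture into its on-treatment categories. A reader who uses T13 or T24 to judge whether the drug had a fair test would be working from an adherence figure that is too low by construction. The size of the shortfall cannot be found from the SAP.

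**Working it through.** The plan states no figure that depends on this rule, so none can be reproduced. The check applies the section 4.3 rule as written.

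**Inputs.** The formulas and the 70% threshold come from section 4.3. One pill per day is implied, because expected pills equal a number of days. Interval lengths are nominal, from the visit schedule in section 3.1 with three months taken as 91 days (an assumption): 7 days (baseline to 1 week), 21 (1 to 4 weeks), 91 − 28 = 63 (4 weeks to 3 months) and 91 (later intervals).

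**Step 1: a compliant participant told to stop.** Someone who takes one pill on each of k days, stops as instructed and returns the rest scores 100 × k / L on an interval of L days. The label is NO when k ≤ 0.70 × L.

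| L (days) | 0.70 × L | Latest k coded NO | Score | First k coded YES | Score |
|---|---|---|---|---|---|
| 7 | 4.9 | 4 | 57.1% | 5 | 71.4% |
| 21 | 14.7 | 14 | 66.7% | 15 | 71.4% |
| 63 | 44.1 | 44 | 69.8% | 45 | 71.4% |
| 91 | 63.7 | 63 | 69.2% | 64 | 70.3% |

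**Step 2: a participant given a prescription and then told not to start or continue.** If no start/continue date exists for this person, the fallback supplies the prescription date and the expected count covers the whole interval. With all pills returned the score is 0/L = 0%, coded NO. The missing-value branch does not catch the case, because a date has been supplied. This step is conditional, since the SAP does not say whether the date is blank in that situation.

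**Step 3: comparison with section 5.3.6.** Take the SAP's 25%/75% example as one prescription interval. The section 4.3 ratio is 23/91 = 25.3% or 16/63 = 25.4%, so the period is labelled non-adherent and the 0.25 goes to category 2. Section 5.3.6 puts it in category 1. The two agree only if the assessment period contains more than one prescription interval. Baseline to 4 weeks, split at the 1-week visit, is an example (7/28 = 25%).

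**Step 4: which outputs are touched.**
- T13 and T25 report the section 4.3 label by arm and are directly exposed.
- Ta and Tna use the same ratio, so a compliant early stopper has Ta = 0 and Tna = 1.
- For T24 and T26, the time proportions already put off-treatment time in its own category. Only the on-treatment share of an early stopper is misfiled.
- The simpler model allowed in section 5.3.6, which drops the time proportions, loses that protection.

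**Step 5: with the denominator ended at the stop.** A compliant stopper scores k/k = 100% for any k ≥ 1. Someone who never started has zero expected pills, so adherence is not applicable.

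**The case against.** The fallback is an ordinary rule for a missing date, and much of what might be built on it goes beyond the SAP. Four stronger readings are tempting, and none is supported.

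- **That a participant told not to continue has no start/continue date by design.** The SAP does not say so. Deviations 5 and 8 treat the instruction as a recorded answer in its own right, and whether it carries a date depends on a CRF that is not shown. Late potassium results are mentioned only for the screening visit, to choose which baseline readings to use. Dispensing before the result is known can be guessed from the two separate dates but is not stated. The 0% case therefore stays conditional.
- **That the error falls mainly on eplerenone.** The potassium check and the hyperkalaemia row in Table T21 make this plausible, but the SAP gives no stop rates by arm. Suppose true adherence is 90% in both arms and the apparent figure is 0.90 × (1 − early-stop rate). Assumed rates of 5% and 1% then give 85.5% against 89.1%, while equal rates give no gap. Mid-interval stops for resolution could occur in either arm.
- **That scoring 1 on both Tna and NToth is an inconsistency.** The indicators are not declared mutually exclusive, and section 5.3.6 expects one period to span several categories.
- **That all of the exploratory analysis is compromised.** The time proportions protect the off-treatment share in T24 and T26.

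It is also fair to say that a stop made at a visit with no new prescription causes no error, that stops after 70% of the interval still score YES, that T10 gives stops by arm as context, and that section 5.2 limits the compliance tables to description.

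These points narrow the concern but do not remove it. The expected-pill formula has no stop term, and the SAP itself recognises part-period treatment in the indicators of section 4.3 and in section 5.3.6.

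**Conclusion.** The point holds as a small error in the adherence denominator. It follows from a stated rule and is not a gap in the plan. A participant who took every pill until an instructed stop is coded non-adherent whenever the stop falls at or before 70% of the interval; on nominal lengths that is day 4 of 7, 14 of 21, 44 of 63 or 63 of 91. The 0% score for someone told not to start rests on the further inference that no start/continue date exists for that person.

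The calculation assumes one pill per day, nominal intervals and return of all unused pills. Neither the number of participants affected nor the direction of any difference between arms can be computed from the SAP. The consequence is confined to descriptive adherence and the exploratory adherence analysis. The modified ITT comparison of BCVA uses no adherence variable and is unaffected.

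**What to change.** In section 4.3:

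1. Define expected pills as days from the start/continue date to the earlier of the next study visit and the recorded date on which the participant was told to stop.
2. Use the prescription date as a substitute only when the participant is recorded as told to start or continue and the date alone is missing.
3. Set adherence to not applicable when expected pills are zero.
4. Apply the same definition to Ta and Tna, so that they agree with the four categories in section 5.3.6, including in the simpler model.

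The change alters no treatment rule and needs no new analysis. It costs a few lines of derivation wording, entered as an amendment under section 1.2, and minor programming that uses stop dates where the CRF records them.

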#### 5.2 Additional descriptive data

Additional tables describing compliance, additional treatments, exposure to steroids, ocular examinations and results of tests performed throughout follow-up, by treatment group will be included (e.g. Tables T4-T15). The choice of summary statistics will be as for the baseline data. These data will only be described; no formal comparisons will be made.

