#### Table T3Patient demography and past history

		Randomised to placebo (n=XX)	Randomised to eplerenone (n=XX)	Overall (n=XX)
Non-ocular history				
Age at randomisation	n (years)			
Male				
Ethnicity	White			
	Black			
	Asian			
	Chinese			
	Mixed			

The VICI study

Other Systolic blood pressure (mmHg) Diastolic blood pressure (mmHg) Heart rate (bpm) TSH/Thyrotropin (mIU/L) Thyroxine (pmol/L) Triiodothyronine (nmol/L) HbA1c (mmol/mol) Haematocrit (Hct) (L/L) Platelets (x10^9 /L) WBC (x109 /L) Serum creatinine (µmol/L) Urea (mmol/L) Potassium (mmol/L) Sodium (mmol/L) Chloride (mmol/L) Bicarbonate (mmol/L) eGFR (ml/min) Bilirubin (µmol/L) ALT (units/L) Albumin (g/L) Protein (g/L) Current Smoking Ex Never Heart failure Myocardial infarction History of angina CCS class No angina L Ш Ш IV NYHA class I Ш Ш IV Transient ischemic attack Stroke DVT ΡE Claudication Diabetes None Diet Oral

	- Neo locallo
	injections
	Insulin
Ocular history	indum
VA score	Low (54-67)
	High (68-85)
CSCR duration (mon	ths)
Family history of CSC	CR
Pupils abnormal ^	
Cornea abnormal^	
Anterior chamber cel	Is present
Anterior chamber flar	re present
IOP measurement (m	nmHg)
Lens status	Phakic
	Pseudophakic
	Aphakic
Nuclear sclerosis	Grade NUC-0
(NUC)*	Grade NUC-1
	Grade NUC-2
	Grade NUC-3
	Grade NUC-9
Cortical (COR)*	Grade COR-0
	Grade COR-1
	Grade COR-2
	Grade COR-3
	Grade COR-9
Central Optical Inv	volvement (CEN)*
Posterior	Grade PSC-0
subcapsular	Grade PSC-1
(PSC)	Grade PSC-2
	Grade PSC-3
	Grade PSC-9
Macula abnormal^	
Peripheries abnorma	^
Disc abnormal^	
Cup disc ratio	
Cataract surgery	
Notes:	

Data are presented as median (interquartile range), mean (standard deviation) or n (%). \* Only completed if lens status was phakic ^ Details of any abnormal clinical findings will be provided in footnotes

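### SAP section 4.3 inverts the triiodothyronine unit conversion, so every converted value in descriptive Tables T3 and T9 would be a million times too large

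*SAP*

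**What the plan says.** The triiodothyronine row of the derivation table in SAP section 4.3 gives three pieces of information:

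- The problem: "Some triiodothyronine measurements have been recorded in pmol/L instead of nmol/L".
- The direction of the conversion: "To convert pmol/L to nmol/L".
- The rule: "Triiodothyronine (nmol/L) = triiodothyronine (pmol/L) * 1000".

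The row label also names nmol/L as the unit of the derived variable. The variable then appears in two output shells, both by randomised group and both in nmol/L. One is the baseline table, Table T3, where the relevant run of rows reads "Thyroxine (pmol/L) Triiodothyronine (nmol/L) HbA1c (mmol/mol". The other is the 12-month visit table, Table T9.

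Section 5.1 summarises continuous baseline data by mean and SD, or by median and IQR when the distribution is skewed, and rules out significance tests for baseline imbalance. Section 5.2 applies the same choice of summary to the follow-up test results and adds: "These data will only be described; no formal comparisons will be made".

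**The concern.** The rule names its source unit, its target unit and its direction, and then applies the factor that belongs to the opposite direction. It is a live instruction: the SAP says that such records exist, so an analyst who programs section 4.3 literally will apply it to real data.

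Converted and directly recorded values share one row in each table. A million-fold error in a subset of that row would give a summary that describes no patient's thyroid function. The SAP prescribes no range check that would catch it.

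**Working it through.** **Inputs**

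- Source unit pmol/L, target unit nmol/L, stated factor 1000: SAP section 4.3.
- 1 pmol = 10^-12 mol and 1 nmol = 10^-9 mol: SI prefixes.
- Planned sample size 104: SAP section 3. Allocation 1:1: SAP section 3.2. Hence 104 / 2 = 52 per arm, used for illustration only.
- Recorded values of 1, 5 and 1500 pmol/L: assumptions. The SAP gives no triiodothyronine values.

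**Step 1. Try to reproduce the stated factor.** The factor from pmol/L to nmol/L is 10^-12 / 10^-9 = 1/1000. The stated factor of 1000 is not reproduced. The reverse conversion, nmol/L to pmol/L, gives 10^-9 / 10^-12 = 1000, so the SAP states the inverse of the conversion that it names.

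**Step 2. Size of the error.** Stated factor over correct factor = 1000 / (1/1000) = 1,000,000. This ratio does not depend on the recorded value.

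**Step 3. Effect on single values, and on an arm mean if one of 52 values is converted.** The shift in the mean is (value under the SAP rule minus correct value) / 52.

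| Assumed record (pmol/L) | SAP rule (nmol/L) | Correct (nmol/L) | Shift in arm mean (nmol/L) |
|---|---|---|---|
| 1 | 1 × 1000 = 1000 | 0.001 | 999.999 / 52 = 19.2 |
| 5 | 5 × 1000 = 5000 | 0.005 | 4999.995 / 52 = 96.2 |
| 1500 | 1500 × 1000 = 1,500,000 | 1.5 | 1,499,998.5 / 52 = 28,846 |

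The shift is in proportion to the assumed record, so only the factor of 10^6 is a finding about the document. The last column also assumes that all 52 patients have a result.

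**Step 4. Median and IQR.** Assume that the wrongly converted values exceed all values recorded directly in nmol/L, as the size of the factor suggests. They then fill the top ranks of the row. In an arm of 52, the upper quartile becomes a converted value once more than about 52 / 4 = 13 are converted, and the median does so once more than about 52 / 2 = 26 are. Below those counts the quartiles and median are displaced only by the change in ranks. The SAP does not say how many values are affected, so it cannot be settled which case applies.

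**Step 5. Look for a repair elsewhere.** No other section gives a different conversion. The amendment log for version 2.0, written after an initial review of data, does not mention the variable.

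**The case against.** The strongest reply concerns consequence, because the arithmetic cannot be defended. Triiodothyronine is not a primary or secondary outcome (sections 2.3 and 2.4) and is not among the model adjustments in section 5.3.1. It occupies one row in each of two descriptive tables, and no planned estimate, confidence interval or p-value draws on it. This stands, and it caps the severity.

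It can also be said that a few values in the thousands would make the distribution plainly skewed, so that section 5.1 would switch the row to median and IQR. This stands in part: the switch softens the error if few values are converted, but it does not make any converted value right, and no count is given.

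Could the asterisk be a misread division sign? This is unlikely. The adherence rule in the same table shows a division and a multiplication side by side, both making sense.

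Three stronger readings are tempting, and the SAP supports none of them:

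- *The error creates a false difference between the arms.* Nothing is said about how converted values fall across the arms, and no formal comparison is planned.
- *The error reaches the treatment effects.* Section 5.3.7 adds a post-hoc adjustment for factors imbalanced at baseline, for outcomes without a baseline measure. It does not list those factors and names no thyroid variable. The route is conceivable but not shown.
- *Results in the two units come from different assays.* Section 4.3 speaks only of the unit in which values were recorded. A residual difference after correct conversion could equally be a mislabelled unit.

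**Conclusion.** The conversion is wrong as written. Every value put through it is 10^6 times too large, and that figure rests on no assumption beyond the meaning of the units.

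The reach is small: the triiodothyronine rows of Tables T3 and T9. There the mean and SD would be badly distorted, and the median and IQR to a degree that depends on an unstated number of converted values. The shift of about 96 nmol/L in an arm mean is an illustration that depends on an assumed record of 5 pmol/L, one converted value and 52 patients per arm. The primary analysis of visual acuity and all other planned treatment comparisons are untouched.

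This should be fixed because the rule is plainly wrong and cheap to correct. A reader might take a million-fold error as a threat to the trial's conclusions, but a variable that is only described cannot carry that weight.

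**What to change.** Replace the multiplication in section 4.3 by a division: value in nmol/L = value in pmol/L / 1000.

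Add one sentence requiring the converted values to be compared with those recorded directly in nmol/L. If the two sets still differ by orders of magnitude, the recorded unit and the measurement should be queried before the values are pooled in Tables T3 and T9. It would also help to state in a table footnote how many values were converted in each arm.

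The cost is one operator, a range check and a footnote. Under section 1.2 the change also needs an entry in the amendment log and re-approval of the SAP. Any data queries that the check raises would be extra work, limited to the affected records.
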